PCI patients requiring OAC [17]. Most recently a scoring system called ABCD-GENE has been developed which allows to readily identify patients with HPR status with high accuracy [18]. In particular, this scoring system integrates clinical (age, body mass index, chronic kidney disease, and diabetes mellitus) and genetic (CYP2C19 alleles) variables. Patients with a high ABCD-GENE score (≥10) have an increased risk of HPR and adverse ischemic events [18]. However, data on the impact on platelet inhibitory effects associated with tailored selection of P2Y₁₂ inhibiting agents in this setting remains unexplored.

5. Specific Aims: The aim of the Switching Anti-Platelet and Anti-Coagulant Therapy (SWAP-AC) – 2 Study is to assess the pharmacodynamic effects of different P2Y₁₂ inhibiting therapy (clopdiogrel vs ticagrelor) according to the ABCD-GENE score in PCI treated patients also requiring OAC.

6. Research Plan:

Study design

This will be a prospective study conducted in any patients with CAD, including those with Acute Coronary Syndrome (ACS) undergoing PCI who have an indication to be treated with an OAC. Patients undergoing PCI treated with DAPT during the peri-PCI period and also require OAC as part of their standard of care will be identified. The study will be performed at the Division of Cardiology of University of Florida Health, Jacksonville, Florida (site PI: [name], PhD) and at St. Antonius Hospital in Nieuwegein, The Netherlands (site PI: [name], MD, PhD).

Patients will be recruited within the Cardiovascular services of each Institution. Patients will be screened by Cardiology Research staff, who will verify that all candidates meet inclusion and exclusion criteria. After providing written informed consent, patients will be stratified according to their ABCD-GENE score (using a cut-off of 10) into two cohorts: ABCD-GENE≥10 and ABCD-GENE< 10. The ABCD-GENE scoring system is described in Figure 1.

Figure 1. ABCD-GENE score

ABCD-GENE SCORE		Points
Clinical factors		
THE	Age >75 years	+4
	BMI >30 kg/m²	+4
6	CKD (GFR <60 mL/min)	+3
(3)	Diabetes mellitus	+3
Genetic factors		
	One CYP2C19 LOF allele	+6
-(3)	Two CYP2C19 LOF alleles	+24

Patients will be screened during hospital stay after undergoing successful PCI.

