Results from blood tests performed within the last 30 days will be considered valid for screening. Patients will undergo genetic testing to identify CYP2C19 genetic status using the Spartan assay or central lab. Randomization will occur once genetic testing results become available, ideally prior to hospital discharge. However, for patients discharged

[figure not shown]
before having results available or over the weekend they will be allowed to return for their randomization within 3 days from test results. Patients with an ABCD-GENE≥10 score will be randomized in a 1:1 fashion to ticagrelor (60 mg/bid) or clopidogrel (75 mg/qd). Patients with an ABCD-GENE<10 will be treated with clopidogrel (75 mg/qd).

Since the choice of P2Y₁₂ inhibitor during the PCI procedure may vary (commercially available agents include clopidogrel, ticagrelor and prasugrel), the following recommendations will be made based on the agent chosen and the treatment assignment: a) patients assigned to clopidogrel and also treated with clopidogrel during PCI will continue with a 75 mg/qd maintenance dose for the duration of the study; b) patients assigned to clopidogrel but treated with ticagrelor or prasugrel during PCI will receive a 600 mg loading dose clopidogrel followed by a 75 mg/qd maintenance dose for the duration of the study; c) patients assigned to ticagrelor and also treated with ticagrelor during PCI will continue with ticagrelor 60 mg bid maintenance dose for the duration of the study; d) patients assigned to ticagrelor but treated with clopidogrel or prasugrel during PCI will be administered a 180 mg loading dose followed by a 60 mg bid for the duration of the study. Administration of randomized treatment will occur prior to hospital discharge as would occur per standard of care for administration of the next dose of P2Y₁₂ inhibiting therapy. The use of a loading dose when switching agent is in line with consensus recommendations for switching P2Y₁₂ inhibiting therapy [19]. The clopidogrel 600mg loading dose and 75 mg/qd maintenance dose regimen is in line with practice recommendations [1]. The ticagrelor 180 mg loading dose regimen is in line with practice guidelines; the 60 mg bid maintenance dose regimen was chosen in light of recent data that this dose provides platelet inhibitory effects not dissimilar from the 90 mg bid dosing

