- Any active bleeding or history of major bleeding
- Ischemic Stroke within 1 month
- Any history of hemorrhagic stroke, or intracranial hemorrhage
- Known non-cardiovascular disease that is associated with poor prognosis (e.g., metastatic cancer) or that increases the risk of an adverse reaction to study interventions.
- End-stage renal disease on hemodialysis

- Known severe liver dysfunction or any known hepatic disease associated with coagulopathy
- History of hypersensitivity or known contraindication to clopidogrel or ticagrelor.
- Systemic treatment with strong inhibitors of both CYP 3A4 and p-glycoprotein (e.g., systemic azole antimycotics, such as ketoconazole, and human immunodeficiency virus [HIV]-protease inhibitors, such as ritonavir), or strong inducers of CYP 3A4, i.e. rifampicin, rifabutin, phenobarbital, phenytoin, and carbamazepine
- Subjects who are pregnant, breastfeeding, or are of childbearing potential, and sexually active and not practicing an effective method of birth control (e.g. surgically sterile, prescription oral contraceptives, contraceptive injections, intrauterine device, double barrier method, contraceptive patch, male partner sterilization)
- Concomitant participation in another study with investigational drug
- Hemoglobin ≤9 mg/dL
- Platelet count <80x10⁶/mL

Genetic Testing

Spartan RX point-of-care rapid genotyping: Spartan RX (Spartan Bioscience Inc., Ontario, Canada) is a point-of-care determining the CYP2C19 (*1,*2,*3,*17) allele status within 1 hour [21,22]. This test consists of four separate steps intended to be done in less than 8 minutes: acquisition of a buccal swab; insertion of the swab into the cartridge; insertion of the reaction solution into the device; and analysis of CYP2C19 genotype triggered by a button on the device. Patients are classified as having or not having a loss of function (LOF) allele status. In particular, patients may be carriers of one (heterozygotes) or two (homozygotes) LOF alleles (*2 or *3) which can be summarized as follows: heterozygotes (*1/*2, *1/*3, *2/*17, *3/*17) or homozygotes (*2/*2, *3/*3 or *2/*3).

Patients without a *2 or *3 LOF (*1/*1, *1/*17 or *17/*17) are defined as non-carriers of LOF alleles [21,22].

Laboratory assessments

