7. Possible Discomforts and Risks

In clinical trials, the most important adverse effect associated with the use of ticagrelor 60 mg was bleeding. The risk of major bleeding with ticagrelor 60 mg was 2.3%; the combined risk of intracranial hemorrhage or fatal bleeding was 0.7% [30]. However, such bleeding prevalence occurred in the setting of long-term trial (median follow-up of 33 months) with bleeding events that accrued over time, while our study is limited to only 30 ± 3 days of therapy. Moreover, these bleeding rates occurred versus placebo, while in our investigation which is being conducted in patients undergoing PCI which mandates the use of a P2Y12 inhibitor per standard of care. Ticagrelor will be compared with clopidogrel, which is also associated with an increased risk of bleeding compared with placebo [31]. However, the rates of bleeding are lower with clopidogrel than with ticagrelor [32]. Dyspnea has been reported as the main non-bleeding side effect with drug discontinuation in 4.6% of patients [30]. Below is a complete lists of potential medication risks:

- Bleeding
- Dyspnea (shortness of breath)
- Headache
- Cough

- Atrial fibrillation
- Mild to moderate diarrhea
- Nausea
- Hypotension (low blood pressure)
- Hypertension
- Dizziness
- Non-cardiac chest pain
- Back Pain
- Fatigue
- Cardiac (heart) chest pain

Patients who discontinue ticagrelor therapy will be switched to clopidogrel. Ultimately, although a 60 mg dosing regimen has not been specifically tested in patients undergoing PCI treated with an OAC, this dosing regimen has shown to be associated with more potent antiplatelet effects than clopidogrel and has not been associated with any increase in thrombotic complications in elective PCI patients conducted in an unselected cohort of subjects [20]. Overall, these considerations limit any safety concerns associated with the conduct of this study.

The risks of the blood draw may include faintness, inflammation of the vein, pain, bruising or bleeding at the site of the puncture. There is also a slight risk of infection from the blood draw.

All clinical events described above, if they were to occur, as well as death, myocardial infarction, stroke, and urgent revascularization procedure with PCI or

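### The hemoglobin exclusion is written in a unit that makes it inoperative: read literally, it excludes nobody

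*Combined protocol and SAP*

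**What the plan says.** The exclusion criteria in section 6 of the combined protocol and SAP (Research Plan, Study population) include "Hemoglobin ≤9 mg/dL". The entry is complete, with a comparison sign, a number and a unit, and shows no sign of redaction or of damage from text extraction. It is the only hemoglobin criterion in the document, and no rationale is given for it.

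The line after it reads "Platelet count <80x10⁶/mL". The same list opens with "Any active bleeding or history of major bleeding" and goes on to exclude prior hemorrhagic stroke or intracranial hemorrhage, and liver disease with coagulopathy.

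Under Study design, the task of applying the list falls to the cardiology research staff, "who will verify that all candidates meet inclusion and exclusion criteria". The laboratory values they use may already be on file: "Results from blood tests performed within the last 30 days will be considered valid for screening".

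**The concern.** An exclusion threshold is an operative rule. Staff screen against it, and anyone who later checks eligibility does the same. If no patient can meet the stated value, the criterion does no work, and an enrolment decision about an anemic patient cannot be classed cleanly as compliant or as a deviation.

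The setting makes this worth correcting. Patients enter on an oral anticoagulant and dual antiplatelet therapy, and continue on the anticoagulant with a P2Y12 inhibitor. Section 7 says that in clinical trials "the most important adverse effect associated with the use of ticagrelor 60 mg was bleeding". The document does not call the hemoglobin line a bleeding safeguard. That is an inference from its place in the list and from the treatments given, though a natural one.

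**Working it through.** This is an eligibility unit error. The plan makes no calculation at this point, so there is no figure of its own to reproduce. The check is a unit conversion.

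**Inputs**
- Hemoglobin limit: 9 mg/dL (section 6, Exclusion criteria).
- Platelet limit: 80 × 10⁶/mL (same list, next line).
- Hemoglobin in living adults: about 2 to 20 g/dL. This is an assumption, deliberately wide, because the document gives no range.

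**Step 1. Convert the limit.** 1 g/dL = 1,000 mg/dL, so 9 mg/dL = 9 / 1,000 = 0.009 g/dL. As 1 dL is one tenth of a litre, this is 0.09 g/L.

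**Step 2. Compare it with possible values.**

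| Assumed hemoglobin | In mg/dL | Ratio to 9 mg/dL | Meets ≤9 mg/dL? |
|---|---|---|---|
| 2 g/dL | 2,000 | 2,000 / 9 = 222 | No |
| 5 g/dL | 5,000 | 5,000 / 9 = 556 | No |
| 9 g/dL | 9,000 | 9,000 / 9 = 1,000 | No |
| 20 g/dL | 20,000 | 20,000 / 9 = 2,222 | No |

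No value in the range meets the criterion, so read literally it excludes 0% of candidates. The result does not depend on where the assumed range ends: even its lowest value is more than 200 times the limit.

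**Step 3. Is this a unit convention used throughout the list?** The platelet limit is 80 × 10⁶/mL / 1,000 = 80,000 per µL, or 80 × 10⁹ per litre, which is a plausible count. The fault is confined to the hemoglobin line.

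**Step 4. Does another section repair it?** The abstract, Study design, Laboratory assessments and section 7 give no second hemoglobin threshold, no other unit and no conversion.

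**Step 5. Does it reach the statistics?** The sample size rests on standard deviations of 55 and 80 PRU, a difference of 90 PRU, 90% power, two-sided alpha of 0.05 and 25% attrition. The primary comparison is an analysis of covariance with the baseline platelet function value as covariate. Hemoglobin enters neither.

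**The case against.** The strongest reply is that this is a self-evident slip. The literal value is physiologically impossible, and the printed unit is one letter away from a unit that would give a plausible value. Trained cardiology staff reading a laboratory report would be unlikely to apply it as printed. This largely stands as a statement about practice: most staff would probably see the slip, and nothing shows that severely anemic patients will in fact be enrolled. It does not make the text correct. Staff who read through the error are applying a criterion that they have supplied themselves.

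A second reply is that the safety stake is limited. The exclusions for active or major bleeding, hemorrhagic stroke or intracranial hemorrhage, hepatic coagulopathy and low platelets still operate. Patients already take an anticoagulant and dual antiplatelet therapy as standard care before entry. The section 7 statement about bleeding concerns ticagrelor 60 mg, assigned to only 20 or 21 of the 84 patients (Study population and the sample size paragraph differ on the number). Clinical events are reviewed by a local safety board. All of this stands, and it limits the weight of the point.

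Two stronger readings are tempting. A reader might infer that the Florida and Netherlands sites would each choose their own unit, so that the populations would differ between sites. The document does not say in which units either site's laboratory reports hemoglobin, and nothing in it suggests that staff would drop the printed unit and apply a bare 9 on another scale. A reader might also infer that the error biases the randomised comparison. Nothing in the document supports that either: the criterion applies before randomisation and plays no part in the analysis.

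**Conclusion.** The point holds as an error in the written eligibility rule. The hemoglobin exclusion equals 0.009 g/dL, no living patient can meet it, and nothing elsewhere in the document corrects it. Its size on the literal text is complete: 0% of candidates excluded. That rests only on the assumption that living adults have hemoglobin well above 0.009 g/dL.

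The consequence is one of compliance and auditability. Under the present wording, enrolling a severely anemic patient is within protocol, and excluding one on hemoglobin grounds is not a protocol rule. The size of any effect on who is actually enrolled cannot be estimated from the document, and may be nil if staff read through the slip. Confidence is high for the unit error and does not extend to any claim about the enrolled population. The correction should be made, but it does not touch the trial's sample size, primary analysis or error rate.

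**What to change.** The sponsor should confirm with the clinical team which hemoglobin threshold and unit are intended, and restate the exclusion in section 6 with both. Any screening or eligibility document that carries the criterion should be checked and made to match; the protocol does not show such a form, so whether it repeats the error is unknown. This review does not propose a value.

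The cost is one line in the next amendment and a check of the screening paperwork. Sample size, randomisation and analysis need no change.

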regimen but with less side effects and more efficacious platelet inhibitory effects than clopidogrel, including after PCI [1,20]. All patients will maintain aspirin 81 mg/qd at least for the duration of hospital stay. Aspirin therapy will be discontinued at time of hospital discharge or at 7 days after PCI at the discretion of the treating physician in patients deemed to be at high ischemic risk, as per standard of care for patients requiring concomitant treatment with a P2Y₁₂ inhibitor and an OAC [14,15].

Assigned treatment will be maintained for 30±5 days. PD assessments will be conducted at 3 time points: i) baseline (while on standard of care DAPT therapy): day after PCI, ideally before the administration of the morning dose of P2Y₁₂ inhibiting therapy and OAC (trough levels of platelet reactivity); however, since patients may get discharged the same day of the PCI or may have already taken their daily dosing regimen, blood sampling will be allowed as this does not interfere with the study hypothesis; patients will continue to take their morning dose of aspirin and all other standard of care therapies; ii) 30±5 days after randomization: before (trough levels of platelet reactivity) and 2 hours after (trough levels of platelet reactivity) the administration of the morning doses of P2Y₁₂ inhibiting therapy and OAC (trough levels of platelet reactivity); patients will take all other standard of care therapies. Figure 2 illustrates the overall study design and a further breakdown of what will occur during the course of the study:

- Patients will first be screened by research personnel to see if they are eligible for the study. Results from blood tests performed within the last 30 days which patients would have performed because of their stent procedure will be considered valid for screening purposes.
- If it is a woman of childbearing potential, a pregnancy test will be done. If the subject is found to be pregnant, their participation in this study will end.
- If they are eligible for the study based on the screening results, they will start the study procedures as outlined below:
 - Genetic test buccal swab. This swab is being done to determine CYP2C19 genetic status.
 - The physician will determine the ABCD-GENE score as described in Figure
 1. This score is calculated by looking at the subject's CYP2C19 genetic

status and clinical information, including age, BMI, renal function, and diabetic status.

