Patients with an ABCD-GENE<10 will be treated with clopidogrel (75 mg/qd). Patients with an ABCD-GENE≥10 score will be randomized in a 1:1 fashion to ticagrelor (60 mg/bid) or clopidogrel (75 mg/qd). Assigned treatment will be maintained for 30 +/- 5 days.

Blood will be collected at two visits by inserting a needle into a vein or from a catheter in a vein. The first visit will be after the PCI ideally before the subject has taken their antithrombotic medications (baseline); however, since patients may get discharged the same day of the PCI or may have already taken their daily dosing regimen, blood sampling will be allowed as this does not interfere with the study hypothesis. The second visit will be 30 +/- 5 days later. At this visit there will be two blood draws: the first before the subject has taken their antithrombotic medication (trough) and second 2 hours after the subject has taken their antithrombotic medication (peak).

PD measures will include a multitude of assays aimed to assess various measures of platelet reactivity, including purinergic and non-purinergic signaling pathways, and thrombin generation, as described below. Although the study will have an open-label design, laboratory personnel will be blinded to treatment assignments. Compliance with antithrombotic therapies will be assessed by interview and pill counting. During study treatment, major adverse cardiac events (death, myocardial infarction, stroke, and urgent revascularization procedures), serious adverse events (bleeding and other adverse events),

as well as non-serious adverse events will be collected. After completing the study, patients will resume an antithrombotic treatment regimen at the discretion of the treating physician.

Study population

A total of 84 CAD patients will be recruited In particular, 42 patients with an ABCD-GENE≥10 will be included and randomized to ticagrelor (n=20) or clopidogrel (n=20), while 42 patients will be in the ABCD-GENE<10 cohort. Patients will need to meet the following study entry criteria:

Inclusion criteria:

- Age \geq 18 years
- Willing and able to provide written informed consent
- Undergone successful PCI and treated with DAPT (aspirin plus a P2Y12 inhibitor) per standard of care
- On treatment with a novel oral anticoagulant (apixaban, dabigatran, edoxaban, or rivaroxaban) for any indication (dosing regimen will be according to standard of care and at the discretion of the treating physician)

Exclusion criteria:

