Peripheral venous blood samples will be drawn through a short venous catheter inserted into a forearm vein and collected in citrate, EDTA, and serum tubes as appropriate for assessments. The first 2-4 mL of blood will be discarded to avoid spontaneous platelet activation. Blood sampling for PD will be performed at 3 time points as described above and shown in the study design section. The following tests will be performed to explore the pharmacodynamic effects of the tested strategies.

- 1. VerifyNow PRU
- 2. Light Transmittance Aggregometry (LTA)
- 3. Whole blood vasodilator-stimulated phosphoprotein (VASP)
- 4. Thrombus Formation Assay (Turbidimetric assay)
- 5. Total Thrombus-Formation Analysis System (T-TAS)

Laboratory assessments including VerifyNow PRU and LTA will be performed within 2 hours of sample collection. VASP and thrombus generation assessments will be performed on stored samples as final batch analysis. Samples will be stored under required refrigerated conditions at the Cardiovascular Research Center of the University of Florida-Jacksonville. Only laboratory staff will have access to the samples. Subject identity will be protected. In particular, samples will be de-identified and data coded. This information will be stored in locked filing cabinets or in computers with security passwords. All laboratory assessments with the exception of thrombin generation measures will be performed at the Cardiovascular Research Center of the University of

Florida-Jacksonville. Thrombus generation assessments will be performed at central core lab (Leeds Institute of Cardiovascular and Metabolic Medicine, University of Leeds, Leeds, UK).

Description of laboratory assays

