- 5) *T-TAS*: T-TAS is an automated microchip flow chamber system for the quantitative analysis of the thrombus formation process under blood flow conditions. T-TAS allows measurement of thrombus formation using the PL/AR-chips (Diapharma, West Chester Township, OH) [17-18]. The PL/AR-chips contains 25 capillary channels (width 40 μm, depth 40 μm) coated with type I collagen and is specifically designed for quantitative analysis of platelet thrombus formation, including platelet adhesion and aggregation, granule secretion, and thrombus growth in the absence of coagulation and fibrinolysis systems. In measurements using the PL/AR-chips, a blood sample collected in a hirudin and sodium citrate containing blood sampling tube. The platelet aggregates gradually increase in size and, in the process, occlude the capillary, resulting in an increase in flow pressure. In the present study, total platelet-derived thrombogenicity is expressed as the area under the flow pressure curve for the first 10 min for the PL/AR-

chips tested at a flow rate of 18 μ L/min (PL18-AUC10). Low PL18-AUC10 reflect reduced thrombus growth and rapid breakdown of the thrombus.

Study endpoints, sample size calculation and statistical analysis

The primary end point of our study will be levels of platelet reactivity, measured as PRU using the VN system, of ticagrelor versus clopidogrel at 30 days after randomization in patients with an ABCD-Gene score ≥ 10 . We hypothesize that ticagrelor 60 mg bid will lead to lower PRU compared with clopidogrel 75 mg qd. Based on previous studies [20], assuming a standard deviation of 55 and 80 PRU for ticagrelor and clopidogrel, respectively, a sample size of 17 patients per treatment group with valid primary end point data will be required to detect an absolute difference of 90 PRU between ticagrelor and clopidogrel with a 90% power and a 2-tailed alpha value of 0.05. Assuming a potential 25% in data attrition due to patient drop-out (e.g., due to side effects, unplanned use of parenteral antiplatelet therapies after randomization or withdrawal of consent) or invalid PD samples (e.g., due to hemolysis or technical reasons), a sample size of up to 21 patients per randomized group; 42 total will be randomized and an additional 42 in the control group. Thus, considering the 3 treatment arms, a total of up to 84 patients are expected to be enrolled to reach the sample size of patients with valid primary end point data required for the primary end point.

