Additional exploratory end points will include the comparisons between clopidogrel-treated patients with ABCD-Gene score<10 and the other 2 arms, as well as comparisons between groups of rates of HPR. For baseline characteristics, categorical variables will be expressed as frequencies and percentages; continuous variables will be

presented as mean ± SD or median [IQR]. Continuous variables will be analyzed for normal distribution with the Kolmogorov-Smirnov test. Comparisons for the primary end point as well as for other intergroup comparisons of continuous variables will be performed with an analysis of covariance with a general linear model with baseline value of the corresponding platelet function test as a covariate. Intragroup comparisons will be performed using a mixed linear model. Comparisons for categorical variables, including rates of HPR will be performed with the Chi square test or Fisher exact test. A p-value < 0.05 will be considered statistically significant. Statistical analysis will be performed with SPSS version 25 software (SPSS Inc.). Data analysis will be performed at the University of Florida. Data transfer will occur in a HIPAA de-identified manner. Data from The Netherlands will arrive coded so that source of data can be easily known."

The PD population will include all patients with PD data and without a major protocol deviation thought to affect significantly the PD of ticagrelor or clopidogrel. The PD population will be used for analysis of all primary and secondary PD variables. Erroneously treated patients (eg, those randomized to one treatment but actually given the other) will be accounted for based on the actual treatment received.

All patients who received at least 1 dose of study drug will be included in the safety population. Safety will be evaluated by assessment of adverse events (including bleeding and ischemic). Adverse events will be collected up to completion of the study. Bleeding events will be classified according to BARC (Bleeding Academic Research Consortium) criteria [27]. Stent thrombosis will be classified according to ARC (Academic Research Consortium) definitions [28]. MI, including peri-procedural MI, will be defined according to the universal definition [29]. Ischemic stroke will be defined as

an ischemic cerebral infarction caused by an embolic or thrombotic occlusion of a major intracranial artery. Death will be considered cardiac in origin unless obvious non-cardiac causes can be identified.

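### Must the plan be changed because the 30-day visit yields two PRU values and neither is named as primary?

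*Combined protocol and SAP*

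**What the plan says.** All references are to section 6, Research Plan, of the combined protocol and SAP.

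- **Endpoint** (Study endpoints, sample size calculation and statistical analysis): the primary endpoint is "levels of platelet reactivity, measured as PRU using the VN system, of ticagrelor versus clopidogrel at 30 days after randomization". The paragraph mentions neither a pre-dose nor a post-dose sample. It plans for a difference of 90 PRU with SDs of 55 (ticagrelor) and 80 (clopidogrel), 90% power and two-sided alpha 0.05, giving 17 evaluable patients per group.
- **Sampling** (Study design): the 30-day samples are taken "before (trough levels of platelet reactivity) and 2 hours after (trough levels of platelet reactivity) the administration of the morning doses". A later paragraph under the same heading describes the same two samples as "the first before the subject has taken their antithrombotic medication (trough) and second 2 hours after the subject has taken their antithrombotic medication (peak", and the bracket closes there.
- **Tests** (Laboratory assessments): "Blood sampling for PD will be performed at 3 time points as described above". VerifyNow PRU is first on the list of tests.
- **Analysis** (Study endpoints): analysis of covariance "with baseline value of the corresponding platelet function test as a covariate". The follow-up draw is not named.
- **Baseline** (Study design): one sample, ideally before dosing; but because patients may go home the same day or "may have already taken their daily dosing regimen, blood sampling will be allowed", it can also be post-dose.
- **Blinding** (Study design): "Although the study will have an open-label design, laboratory personnel will be blinded to treatment assignments".

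**The concern.** A single primary test at 5% requires one value per patient, and the endpoint wording fits two. Platelet reactivity at the end of a dosing interval and 2 hours after a dose are different quantities, so the estimate, and possibly the p-value, depends on the draw. The trial is open-label, and the plan says nothing on whether the analyst is blinded. If someone looked at both comparisons and reported the better one as primary, the stated alpha would no longer describe the test. The Study design text adds to the doubt by labelling both 30-day samples as trough, so the labels there cannot be used to work out which draw was meant.

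**Working it through.** **1. Does any other text identify the draw?** The hypothesis sentence and the sample-size sentence mention neither trough nor peak. The covariance model names only the baseline covariate; baseline is a single sample that may be pre- or post-dose, so it does not settle the follow-up draw. The mixed model is reserved for within-group comparisons. No text averages the two draws or adjusts for multiplicity. Figure 2 was not available for this check; it is described as showing the overall design, and the endpoints section does not refer to it. On the available text, the draw is unnamed.

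**2. The plan's own sample size.** The formula is n per group = 2 × (1.960 + 1.282)² × SD² / 90².

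- With SD² = (55² + 80²)/2 = 4712.5 (SD 68.65): n = 2 × 10.51 × 4712.5 / 8100 = 12.2, so 13. The noncentral t version gives 14.
- With SD 80 in both arms: n = 2 × 10.51 × 6400 / 8100 = 16.6, so 17, which matches the stated figure.

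The stated 17 is therefore conservative for the stated SDs. At 17 per group the standard error is √((55² + 80²)/17) = 23.5 and 90/23.5 = 3.82. Power is 96.9% by the normal approximation and 95.8% by the Welch noncentral t.

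**3. Error rate if the draw were chosen afterwards.** Let Z1 and Z2 be the adjusted test statistics for the two draws, jointly normal with correlation r, with no true difference at either draw. The two-sided rate is P(|Z1| > 1.96 or |Z2| > 1.96). The rate in the hypothesised direction counts only the tail with ticagrelor lower. The documents give no value for r, so all values here are assumed.

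| r (assumed) | Two-sided | Hypothesised direction only |
|---|---|---|
| 0 | 9.75% (= 1 − 0.95²) | 4.94% (= 1 − 0.975²) |
| 0.5 | 9.07% | 4.54% |
| 0.7 | 8.35% | 4.17% |
| 0.8 | 7.81% | 3.90% |
| 0.9 | 7.04% | 3.52% |
| One draw fixed beforehand | 5% | 2.5% |

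For non-negative r, 9.75% is the ceiling.

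**4. How often would the choice change the answer?** Suppose the planned 90 PRU and SDs of 55 and 80 held at both draws. Each test then misses with probability 1 − 0.958 = 0.042. The chance that exactly one of the two is significant is at most 0.042 + 0.042 = 8.4%, whatever the correlation. If the tests were independent it would be 2 × 0.958 × 0.042 = 8.0%, and positive correlation makes it smaller.

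**The case for a change.** The strongest case for a change is that this is the trial's only confirmatory test, that naming the draw takes one sentence, and that three consequences need no assumption of bad faith.

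- **The reported estimate depends on the draw.** True. Whichever draw is used, though, the planned analysis is a valid 5% test provided the draw is set before the arms are compared. The plan contains no rule that picks the draw from the results.
- **A patient may have one usable and one spoiled 30-day sample, so valid primary data is undefined until the draw is known.** Also true. Laboratory staff are blinded to treatment assignment, however, so a sample they reject for hemolysis or technical failure at either draw is not rejected with knowledge of the arm. Once the draw is fixed, evaluability follows.
- **The 90 PRU and the SDs may come from one draw while the other is analysed.** This is the most substantial of the three. With the SDs unchanged, Welch power at 17 per group is 91% for a true difference of 80 PRU, 82% for 70, 69% for 60 and 54% for 50. These differences are assumed; nothing in the documents shows that the planned 90 PRU fails at either draw. The point is a missing source note, not a demonstrated shortfall.

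The mismatch of trough and peak labels is a wording slip. Both descriptions give the same sampling times, and the later one labels them consistently.

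**Conclusion.** The gap in the text is real, but it does not call for a change. The plan states no rule that gives a wrong result; it leaves out a definition that a competent analyst would write down before comparing the arms. The preferred pre-dose timing of baseline makes the pre-dose draw a natural reading, although the text does not compel it, and the post-dose draw would serve equally well for error control.

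The possible harm is about 2 to 4 percentage points on the two-sided 5% (7.04% to 9.07% for assumed correlations of 0.9 to 0.5), or 1 to 2 points on 2.5% in the hypothesised direction. It requires both that the draw is chosen after seeing the two results and that there is no true difference at either draw. The second condition is remote from the plan's own premise of a 90 PRU difference. Under that premise at both draws, the two would disagree on significance at most 8.4% of the time. Section 8 also says the study is not designed to evaluate differences in clinical benefit, which limits what a false claim could lead to. The conclusion assumes that the draw is settled before any comparison by arm, and that Figure 2 does not contradict the text.
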